### 11.1.4. Recording Adverse Events

All AEs must be recorded in the source documents and in the eCRFs provided by the Sponsor from the signing of the Informed Consent Form (ICF) until the end of study participation. AEs will be assessed for likelihood of causal relationship to the study drug (EP262 or placebo) and severity.

The new onset of signs, symptoms, or other findings that occur before signing of the ICF will be captured as medical history (Section 11.3).

### 11.1.4.1. Special Instructions for Recording Adverse Events in the eCRF

#### **Diagnosis versus Signs and Symptoms**

If a diagnosis is known at the time of reporting, this should be recorded in the eCRF rather than the individual signs and symptoms (eg, record only hepatitis rather than elevated transaminases, bilirubin, and jaundice). However, if a constellation of signs and/or symptoms cannot be medically characterized as a single diagnosis or syndrome at the time of reporting, each individual event should be recorded as an SAE or AE on the eCRF. If a diagnosis is subsequently established, it should be reported as follow-up and should replace the individual signs and/or symptoms as the event term on the eCRF, unless the signs/symptoms are clinically significant.

### **Adverse Events Occurring Secondary to Other Events**

In general, AEs occurring secondary to other events (eg, clinical sequelae or a cascade of events) should be identified by their primary cause. For example, if severe vomiting is known to result in dehydration, it is sufficient to record only vomiting as an SAE or AE on the eCRF. However, medically significant AEs occurring secondary to an initiating event that are separated in time should be recorded as independent events on the eCRF. For example, if severe vomiting leads to acute renal failure, both events should be recorded on the eCRF.

#### **Persistent or Recurrent Adverse Events**

A persistent AE is one that extends continuously, without resolution, between subject evaluation timepoints. Such events should only be recorded once on the eCRF. If a persistent AE becomes more severe or lessens in severity, it should be recorded as a new AE on the eCRF.

A recurrent AE is one that occurs and resolves between subject evaluation timepoints, and subsequently recurs. Each reoccurrence of an AE should be recorded on the eCRF.

#### **Abnormal Laboratory Values or Vital Signs**

Protocol defined laboratory values and vital signs will be reported as AEs if the abnormal laboratory or vital sign result:

- Requires an adjustment in the study drug(s) or discontinuation of treatment;
- Requires additional testing, excluding repeat testing of the lab in question, or surgical intervention;
- Is associated with accompanying signs/symptoms that are not considered part of a preexisting diagnosis or syndrome; or
- Is considered clinically significant by the Investigator

If an abnormal laboratory value or vital sign is the result of an evaluation of clinical signs, symptoms, or suspected diagnosis during the conduct of the study, the signs/symptoms or diagnosis should be reported as an AE (or if appropriate, an SAE) only if clinically significant, and the associated laboratory value or vital sign should be considered additional information that must be collected on the relevant eCRF.

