#### 11.1. Adverse Events

#### 11.1.1. Definition of an Adverse Event

An AE is defined as any untoward medical occurrence in a subject administered a pharmaceutical product and which does not necessarily have a causal relationship with this treatment. An AE can therefore be any unfavorable or unintended sign (including a clinically significant abnormal laboratory finding), symptom, or disease temporally associated with the use of a medicinal (investigational) product.

Medical conditions present at baseline that worsen in severity or frequency after exposure to study drug are considered TEAEs. A TEAE is any condition that was not present prior to treatment with the study drug but appeared following treatment, was present at treatment initiation but worsened during treatment, or was present at treatment initiation but resolved and then reappeared while the individual was on treatment (regardless of the intensity of the AE when the treatment was initiated). Planned hospital admissions or surgical procedures for an illness or a disease that existed before administration of study drug, and for which the condition has not worsened since starting study drug, are not to be considered TEAEs/treatment-emergent SAEs. Events with emergency room visits that are less than 24 hours will also not be considered SAEs unless they meet one of the criteria listed in Section 11.2.1.

Clinically significant abnormal laboratory tests, 12-lead ECG assessments, or vital sign results may constitute an AE if they meet one of the criteria listed in Section 11.1.4.1. However, whenever possible, the underlying diagnosis should be listed in lieu of associated abnormal results. Abnormalities deemed not clinically significant by the Investigator should not be reported as AEs.

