4.5.5 Clinical Laboratory Evaluation

All descriptive summaries of laboratory results will be based on data analyzed by the central laboratory and presented in conventional units. All data will be included in by-subject data listings. Laboratory measurements identified as abnormal (i.e., outside the normal range) will also be listed separately by subject, laboratory test, and unit. In addition, normal ranges provided by the central laboratory will be presented in a separate listing.

Clinical laboratory measurements, including serum chemistry, hematology, and coagulation will be summarized by treatment group and overall subjects combined. Descriptive statistics will be presented for observed values and changes from baseline at each visit where parameters were scheduled to be collected per the clinical study protocol.

Where applicable, laboratory results will be classified as “low,” “normal,” or “high” with respect to the parameter-specific reference ranges (i.e., below the lower limit of the normal range, within the normal range, or above the upper limit of the normal range). Three-by-three contingency tables will be presented for each laboratory parameter to summarize the shift from the baseline category to the worst post-baseline measurement, defined as the value numerically farthest outside of the normal range across all post-baseline visits through the end of the study. Summary results will include the count and percentage of subjects within each shift category and treatment group and overall subjects combined.

The clinical study protocol includes guidance associated with the monitoring and interruption of study drug for suspected DILI. Subjects with the following post-baseline ALT or AST values will be assessed for the following DILI criteria:

- ALT or AST $>8 \times$ ULN
- ALT or AST $>5 \times$ ULN for more than 2 weeks: subjects must have confirmed elevated values by subsequent repeat testing that shows at least two weeks of elevated values.
- ALT or AST $>3 \times$ ULN AND total bilirubin $>2 \times$ ULN OR INR >1.5
- ALT or AST $>3 \times$ ULN with the appearance of new onset fatigue, nausea, vomiting, right upper quadrant pain or tenderness, fever, rash, and/or eosinophilia ($>5\%$).

Subjects qualifying in any of the above treatment-emergent DILI criteria will be presented in a data listing.

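### Protocol 11.1.4.1 reports a symptom or diagnosis as an AE only if clinically significant once its work-up gives an abnormal result, which conflicts with 11.1.1 and 11.1.4 and can understate TEAE incidence

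*Protocol*

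**What the plan says.** Protocol 11.1.1 defines the event: "An AE can therefore be any unfavorable or unintended sign (including a clinically significant abnormal laboratory finding), symptom, or disease temporally associated" with use of the product. In that sentence clinical significance attaches to the laboratory finding alone. A later sentence, "Abnormalities deemed not clinically significant by the Investigator should not be reported as AEs", stands in the paragraph on laboratory, ECG and vital-sign results.

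Protocol 11.1.4 then says "All AEs must be recorded in the source documents and in the eCRFs provided by the Sponsor", from consent until participation ends. In 11.1.2, Grade 1 takes in mild symptoms that need no intervention.

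Protocol 11.1.4.1, under Abnormal Laboratory Values or Vital Signs, has two parts. A list of four conditions decides when an abnormal value is itself reported as an AE; the third reads "Is associated with accompanying signs/symptoms that are not considered part of a preexisting diagnosis or syndrome". The closing paragraph covers values obtained while evaluating a sign, symptom or suspected diagnosis. There, "the signs/symptoms or diagnosis should be reported as an AE (or if appropriate, an SAE) only if clinically significant". The same sentence keeps the test result on the eCRF, but only as supporting data for the event and not as an event of its own.

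SAP 4.5.3 builds every TEAE table from the AEs that were reported. SAP 3.4.4.1 refers back to protocol 11.1.4.1 for abnormal results.

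**The concern.** The closing paragraph moves a condition that elsewhere belongs to test results onto the symptom or diagnosis itself. The protocol does not say what clinically significant means for a symptom, so each investigator has to decide. The extra hurdle applies when the work-up was abnormal, where one would expect more recording rather than less.

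The first-listed primary endpoint is the kind, number and severity of TEAEs. An event that never becomes an AE record cannot appear in any SAP 4.5.3 table. Two sites that both follow the protocol, one guided by 11.1.1 and one by the closing paragraph of 11.1.4.1, could handle the same mild symptom differently.

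**Working it through.** **1. One mild symptom under each rule.** Take mild, Grade 1 nausea that starts after the first dose.

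| Situation | Governing text | AE record for the nausea? |
|---|---|---|
| No abnormal value from a work-up | 11.1.1, 11.1.4 | Yes |
| Work-up gives an abnormal value; nausea judged clinically significant | 11.1.4.1, closing paragraph | Yes, with the value as supporting information |
| Work-up gives an abnormal value; nausea judged not clinically significant | 11.1.4.1, closing paragraph | No; only the value is kept |
| Abnormal value from a routine draw, not from a symptom work-up | 11.1.4.1, list of conditions, for the value; 11.1.1 for any symptom | The closing paragraph does not apply |

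The first and third rows hold the same event with opposite results. The third row conflicts with 11.1.4, which makes no exception, and with a severity scale whose lowest grade is meant for such events.

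**2. Whether anything later recovers the event.** The third condition in the list could bring the abnormal value in as a laboratory AE. The next paragraph, however, treats that value as additional information, and a laboratory term would still not count as nausea. SAP 4.5.3 works from reported AEs, and SAP 4.5.6.3 provides no listing of physical examination results. The values themselves are safe: SAP 4.5.5 lists abnormal results, and the change-from-baseline summaries, also part of the primary endpoint, do not depend on this rule.

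**3. Scale.** The plan gives no TEAE rate and no sample size calculation, so there is no stated figure to reproduce. The inputs are about 30 subjects in a 2:1 ratio (protocol 7.4 and 9.1).

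- Arm sizes: 30 × 2/3 = 20 on EP262 and 30 × 1/3 = 10 on placebo.
- One subject whose only TEAE is unrecorded lowers TEAE incidence by 1/20 = 5.0 percentage points on EP262, 1/10 = 10.0 points on placebo, and 1/30 = 3.3 points overall.
- The frequent-event tables in SAP 4.5.3 start at 10% of the Safety Analysis Set. 3/30 = 10.0% is shown and 2/30 = 6.7% is not, so one unrecorded subject can take a term out of such a table. The term stays in the full table by system organ class and preferred term.

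These are the effects of one lost subject. They are not estimates of how many would be lost.

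**The case against.** The closing paragraph can be read as a rule against double counting: record the clinical event and attach the test result to it. That fits 11.1.1, which prefers the underlying diagnosis to the abnormal result. On this reading, treating the value as additional information does not contradict the third condition in the list, because the specific case overrides the general one. This part of the objection stands. It does not explain why the symptom or diagnosis should also have to be clinically significant.

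Similar wording occurs elsewhere. Protocol 11.6 and SAP 4.5.6.3 apply clinical significance to physical examination findings, so correcting one sentence alone would leave the plan uneven. The related clause in 11.1.4.1 on symptoms later replaced by a diagnosis is harmless here, since the diagnosis is still recorded.

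Three stronger readings are tempting, and the documents do not support them:

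- **A reader might infer that the liver listing will miss subjects** on the criterion requiring ALT or AST above 3 times ULN "with the appearance of new onset fatigue, nausea, vomiting, right upper quadrant pain or tenderness, fever, rash" or eosinophilia. SAP 4.5.5 does not say that the symptom part comes only from AE records. Protocol 11.10.3 separately asks for a physical examination and AE information at such elevations. Chemistry is also drawn at every visit, and a value from a routine draw falls outside the closing paragraph.
- **A reader might infer that SAEs would be lost**, because the sentence mentions them. Protocol 11.2.1 defines an SAE by criteria without this filter, and 11.2.2 requires a form for each one. An event meeting those criteria would hardly be judged not clinically significant.
- **A reader might attach a probability to a term leaving the frequent-event table.** That needs the share of cases with an abnormal work-up and the share of those judged not significant. The documents give neither. Applying an assumed withholding rate to every case of a term would overstate the effect, because the rule reaches only some of them.

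**Conclusion.** The conflict is real and lies in one phrase: the clinical-significance condition on signs, symptoms and diagnoses. As written it allows mild TEAEs to go unrecorded, so absolute TEAE incidence can be understated.

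The reach is limited to events whose work-up gives an abnormal laboratory value or vital sign. The number lost cannot be determined from the documents. With 20 and 10 subjects, each subject whose only TEAE is lost costs 5 or 10 percentage points in that arm.

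A reader might infer bias in favor of EP262. Nothing in the documents shows it. Investigators are blinded (protocol 9.3.2), so the loss should be similar between arms in expectation. That rests on EP262 not itself changing how often work-ups are abnormal, and protocol 5.2 reports no adverse laboratory or vital-sign trends in the healthy-subject study. A similar proportional loss would still lower both rates and tend to shrink any difference between them.

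**What to change.** In the closing paragraph of protocol 11.1.4.1, remove the clinical-significance condition as it applies to signs, symptoms and diagnoses. State that any of these meeting the 11.1.1 definition is recorded as an AE, and as an SAE if an 11.2.1 criterion is met. Keep the linked value as additional information, and keep the significance filter for isolated test results.

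Align protocol 11.6 and SAP 4.5.6.3 with the same rule, and carry it into the eCRF completion guidance.

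The cost is a short protocol and SAP text change, plus a few more mild TEAEs reported in both arms. No analysis method changes.

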#### 11.2. Serious Adverse Events

#### 11.2.1. Definition of a Serious Adverse Event

An SAE is any untoward medical occurrence, that at any dose:

- Results in death;
- Is life-threatening, ie, the subject is, in the opinion of the Investigator, at immediate risk of death from the event as it occurred, (it does not include an event that, had it occurred in a more severe form, might have caused death);
- Requires hospital admission or prolongs hospitalization. Planned hospital admissions
  or surgical procedures for an illness or a disease that existed before administration of
  study drug, and for which the condition has not worsened since starting study drug,
  are not to be considered SAEs. Emergency room visits that are less than 24 hours will
  also not be considered SAEs unless any of the other serious criteria is fulfilled;
- Results in persistent or significant disability or incapacity;
- Is a congenital anomaly/birth defect; or
- Is a medically significant event that, based on appropriate medical judgment, may jeopardize the subject and may require medical or surgical intervention to prevent one of the outcomes listed above.

Note: A distinction should be drawn between SAEs and severe AEs. Severity is a measure of the intensity of an AE, while the criteria for seriousness are indications of adverse subject outcomes for regulatory reporting purposes. A severe AE is not necessarily considered an SAE. For example, a headache that persists for several hours may be considered a severe AE but not an SAE. Conversely, a wound infection that may be considered minor could be an SAE if it prolonged hospitalization.

### 11.2.2. Reporting Serious Adverse Events

The Investigator and the Sponsor will monitor safety for this study. A Serious Adverse Event Report (SAER) Form is to be completed for each SAE occurring after signing of the ICF until 30 days after the last dose of study drug, regardless of causality.

All SAE reports must be reported	d within 24 hours of the Investigator's kr	nowledge of the
event to	. If requested by the Spor	nsor, any supporting
documentation (eg, medical recor	ds) sent to	with the
SAER Form must have subject id-	lentifying information (eg, subject names, s	ubject addresses,
medical records number) redacted	d by the site. Follow-up information to all S	SAEs should be
submitted to the Sponsor, or design	gnee, in the same timeframe as initial report	ts.

All SAEs will be followed until resolution or medical stabilization (in cases where resolution would not be expected).

In accordance with applicable regulations and local laws, the Sponsor or designee will report all serious and unexpected AEs assessed as related to study drug by the Investigator and/or Sponsor, to the regulatory authorities within the required timeframe. The Investigator will be responsible for reporting this safety information to his or her IRB/IEC.

If the Investigator becomes aware of an SAE any time after study completion and determines it is related to the study drug, the SAE must be reported to the Sponsor or designee within 24 hours of the Investigator's knowledge of the SAE.

### 11.2.3. Pregnancy

Pregnancy in and of itself is not an AE, although pregnancies occurring in subjects or partners of male subjects are considered immediately reportable events. If a pregnancy occurs in a subject, study drug must be discontinued immediately. The pregnancy must be reported to Drug Safety via email at within 24 hours of the Investigator's knowledge of the pregnancy using the Pregnancy Reporting Form.

The Investigator will follow the pregnant woman until completion of the pregnancy, and must notify the Sponsor, or designee, of the outcome within 24 hours of the Investigator's knowledge of the pregnancy outcome. The Investigator will provide this information on the Pregnancy Reporting Form. This notification includes pregnancies resulting in live, "normal" births.

If the pregnant subject experiences an SAE during pregnancy, or the outcome of the pregnancy meets the criteria for immediate classification as an SAE (ie, spontaneous abortion [any congenital anomaly detected in an aborted fetus is to be documented], stillbirth, neonatal death, or congenital anomaly), the Investigator should follow the procedures for reporting SAEs (ie, report the event to the Sponsor via email at within 24 hours of the Investigator's knowledge of the event).

All neonatal deaths and congenital anomalies that occur within 30 days of birth (regardless of causality) should be reported as SAEs to the Sponsor or designee. In addition, any infant death or congenital anomaly occurring after study completion that the Investigator suspects is related to the in-utero exposure to the study drug should also be reported to the Sponsor or designee.

# 11.3. Medical History

The Investigator or designee will collect and review the subject's medical history, including AD disease history, to evaluate the subject's eligibility for study participation. The new onset of signs, symptoms, or other findings that occur from before signing of the ICF will be captured as medical history.

# 11.4. Vital Signs

Vital signs, including sitting systolic and diastolic blood pressure, pulse rate, body temperature, and respiratory rate, will be measured predose (as applicable) after at least 5 minutes of rest. Vital signs are to be performed predose if the dose is administered at the site.

### 11.5. Body Weight and Height

Body weight should be measured with no shoes and heavy clothing (outdoor clothing such as coats) on and using a calibrated scale throughout the study. Height should be measured using a stadiometer with no shoes.

### 11.6. Physical Examinations

Physical examinations will include but are not limited to an assessment of general appearance, skin, HEENT (head, eyes, ears, nose, throat), musculoskeletal, thyroid/endocrine, cardiovascular, chest/lung, neurologic, abdomen, and extremities/general body systems.

Abbreviated, symptom directed physical examinations to assess clinically significant changes from Screening or any new signs or symptoms will be conducted at Visit 3 (Week 3), Visit 5 (Week 10), and the Early Treatment Termination Visit, and may be conducted at other visits as determined by the Investigator based on subject complaint.

Clinically significant abnormalities from before signing of the ICF will be recorded as medical history, and clinically significant changes after signing the ICF will be recorded as AEs.

### 11.7. Standard 12-Lead Electrocardiograms

Twelve-lead ECGs are to be performed predose (as applicable) with subjects in a supine position after at least 5 minutes of rest. An ECG is to be performed predose if the dose is administered at the site.

## 11.8. Laboratory Evaluations of Safety

Samples for the following laboratory tests should be collected after an overnight fast (at least 8 hours):

- Chemistry: sodium, albumin, alkaline phosphatase (ALP), bicarbonate, calcium, corrected calcium, chloride, bilirubin (total, indirect, and direct), AST, ALT, blood urea nitrogen, urea, creatinine, glucose, magnesium, phosphorus, potassium, creatine phosphokinase, total cholesterol, triglycerides, high-density lipoprotein cholesterol, low-density lipoprotein cholesterol, lactate dehydrogenase, gammaglutamyltransferase, and total protein
- Hematology: hemoglobin, hematocrit, mean corpuscular hemoglobin, mean corpuscular hemoglobin concentration, mean corpuscular volume, white blood cell count (total and differential), red blood cell count, platelet count, and platelet volume
- Urinalysis: leukocyte esterase, nitrites, pH, protein, specific gravity, glucose, occult blood, ketones, bilirubin, and urobilinogen; microscopic analysis is to be performed only if protein, leukocyte esterase, blood or nitrite is positive
- Coagulation: activated partial thromboplastin time, international normalized ratio (INR), and prothrombin time
- Pregnancy testing: required for all females; serum test at Screening (Visit 1) and urine test for all other visits where pregnancy testing is required

The urine pregnancy test for female subjects will be conducted locally; all other planned laboratory evaluations of safety will be conducted at a central laboratory. Details for sample collection, processing, storage, and shipment will be provided in the Laboratory Manual.

